#### 3.3.1 DATA SAFETY & MONITORING BOARD

An independent Data Safety & Monitoring Board (DSMB) will provide safety oversight. The DSMB will meet quarterly to review safety data. The DSMB will be charged with advising the Sponsor if there appears to be a safety issue. No formal interim analysis is planned. The following stopping rules will be applied:

- If at any time during the study one-third (1/3) or more of the subjects experience an Adverse Event of Special Interest, further enrollment and study treatment will be halted immediately until a thorough investigation has been conducted by the Medical Monitor, Principal Investigator for the trial, and the DSMB.
- If any SAE (or potentially life-threatening AE) or death assessed as related to study treatment occurs, further enrollment and study treatment will be halted immediately until a thorough investigation has been conducted by the Medical Monitor, Principal Investigator for the trial, IRB (if applicable) and the DSMB.
- If three or more subjects in this study experience the same Grade 3 or 4 adverse event, assessed as related to study treatment, further enrollment and study treatment will be halted immediately until a thorough investigation has been conducted by the Medical Monitor, Principal Investigator for the trial, and the DSMB.

- In the event of two identical, unexpected, Grade 4 toxicities, assessed as related to study treatment, further enrollment and study treatment will be halted immediately until a thorough investigation has been conducted by the Medical Monitor, Principal Investigator for the trial, IRB (if applicable) and the DSMB.

The sponsor or designee will notify all investigators and IRBs/EC (if required) regarding the outcome of any investigation stemming from a Study Pause.

### 3.4 IMMUNOGENICITY ASSESSMENT

The study will explore humoral and cell mediated immune responses to VGX-3100 in blood samples taken at baseline (both Screening as well as Day 0 prior to dosing) and at Weeks 15, 27, 48, 74 and 96. Vulvar samples will also be analyzed for evidence of immune responses at Screening and at Weeks 48, 74 and 96.

A blood sample from one time point during the study will be tested to explore the relationship between subject HLA types and regression.

### 3.5 VIROLOGIC ASSESSMENT

Tissue samples will be obtained to characterize HPV infection at Screening, Week 48, 74 and 96. Cervical samples, oropharyngeal (OP) rinse samples, vaginal, and intra-anal tissue swab samples will be obtained to characterize HPV infection in samples from study subjects taken at Screening (cervical sample only), Day 0 prior to dosing (OP, vaginal and intra-anal only) and at Weeks 27, 48, 74 and 96.

If there is residual tissue in the paraffin block after histologic diagnoses have been rendered, then unstained slides and/or the relevant paraffin blocks will be collected for immunohistochemistry (IHC) and in situ hybridization (ISH) for the presence of HPV-16/18. Whenever possible, these studies will be performed on tissue sections from the diagnostic biopsy (pre-dose) and from tissue obtained post-dose (Week 48, 74 and 96).

## 4. SELECTION OF SUBJECTS

### 4.1 INCLUSION CRITERIA

Each subject must meet all of the following criteria to be enrolled in the study:

1. Must understand, agree and be able to comply with the requirements of the protocol. Subjects must be willing and able to provide voluntary consent to participate and sign a Consent Form prior to study-related activities;
2. Women aged 18 and above;
3. Confirmed vulvar infection with HPV types 16 and/or 18 at screening;
4. Vulvar tissue specimen/slides provided to Study Pathology Adjudication Committee for diagnosis must be collected within 10 weeks prior to anticipated date of first dose of study drug;
5. Histologic evidence of vulvar HSIL as confirmed by PAC at screening;
6. Must be judged by investigator to be an appropriate candidate for the protocol-specified

- procedure (i.e. excision or biopsy) required at Week 48;
7. Must have vulvar HSIL that is accessible for sampling by biopsy instrument and of adequate size to ensure that a visible lesion remains after 4 mm screening biopsy;
  8. Must have vulvar HSIL that can be completely demarcated for area measurement;
  9. Must meet one of the following criteria with respect to their reproductive capacity:
    - a. Is post-menopausal as defined by spontaneous amenorrhea for more than 12 months or spontaneous amenorrhea for 6-12 months with FSH level >40 mIU/mL;
    - b. Is surgically sterile due to absence of ovaries or due to a bilateral tubal ligation/occlusion performed more than 12 months prior to screening;
    - c. Women of Child Bearing Potential (WOCBP) are willing to use a contraceptive method with failure rate of less than 1% per year when used consistently and correctly from screening until 6 months following the last dose of investigational product. Acceptable methods are the following:
      - i. Hormonal contraception: either combined or progestin-alone including oral contraceptives, injectable, implants, vaginal ring, or percutaneous patches. Hormonal contraceptives must not be used in subjects with a history of hypercoagulability (e.g., deep vein thrombosis, pulmonary embolism);
      - ii. Abstinence from penile-vaginal intercourse when this is the subject's preferred and usual lifestyle;
      - iii. Intrauterine device or intrauterine system;
      - iv. Male partner sterilization at least 6 months prior to the female subject's entry into the study, and this male is the sole partner for that subject.
  10. Normal screening electrocardiogram (ECG) or screening ECG with no clinically significant findings as judged by the investigator.

## 4.2 EXCLUSION CRITERIA

Subjects meeting any of the following criteria will be excluded from the study:

1. Untreated microinvasive or invasive cancer;
2. Biopsy-proven Vaginal Intraepithelial Neoplasia (VAIN) and are not undergoing treatment for VAIN;
3. Biopsy-proven Anal Intraepithelial Neoplasia (AIN) and are not undergoing treatment for AIN;
4. Biopsy-proven Cervical Intraepithelial Neoplasia (CIN) 2/3 and are not undergoing treatment for CIN;
5. Biopsy-proven differentiated VIN;
6. More than 10 weeks have elapsed between date of initial tissue biopsy for screening and day of first dose (i.e. Day 0);
7. Vulvar HSIL that is not accessible for sampling by biopsy instrument;
8. Vulvar HSIL that is not of adequate size to ensure that a visible lesion remains after biopsy;

9. Cervical lesion(s) that cannot be fully visualized on colposcopy due to extension high into cervical canal at screening;
10. History of endocervical curettage (ECC) which showed cervical HSIL indeterminate, or insufficient for diagnosis (ECC is not performed as part of study screening) and did not receive definitive treatment;
11. Treatment for genital warts within 4 weeks prior to screening;
12. Any previous treatment for vulvar HSIL (e.g. with surgery and/or imiquimod) within 4 weeks prior to screening;
13. Allergy to imiquimod 5% cream or to an inactive ingredient in imiquimod 5% cream;
14. Is pregnant, breastfeeding or considering becoming pregnant within 6 months following the last dose of investigational product;
15. Presence of any abnormal clinical laboratory values greater than Grade 1 per Common Toxicity Criteria for Adverse Events (CTCAE) v 4.03 within 30 days prior to Day 0 or less than Grade 1 but deemed clinically significant by the investigator;
16. Immunosuppression as a result of underlying illness or treatment including:
  - a. History of or positive serologic test for HIV at screening;
  - b. Primary immunodeficiencies;
  - c. Long term use ( $\geq 7$  days) of oral or parenteral glucocorticoids at a dose of  $\geq 20$  mg/day of prednisone equivalent (use of inhaled, nasal, otic, and ophthalmic corticosteroids are allowed);
  - d. Current or anticipated use of disease modifying doses of anti-rheumatic drugs (e.g., azathioprine, cyclophosphamide, cyclosporine, methotrexate) and biologic disease modifying drugs such as TNF- $\alpha$  inhibitors (e.g. infliximab, adalimumab or etanercept);
  - e. History of solid organ or bone marrow transplantation;
  - f. Any prior history of other clinically significant immunosuppressive or clinically diagnosed autoimmune disease that may jeopardize the safety of the subject or require therapy that would interfere with study assessments or endpoint evaluation, or otherwise impact the validity of the study results.
17. History of previous therapeutic HPV vaccination (licensed prophylactic HPV vaccines are allowed, e.g. Gardasil®, Cervarix®);
18. Received any non-study related non-live vaccine within 2 weeks of Day 0;
19. Received any non-study related live vaccine (e.g. measles vaccine) within 4 weeks of Day 0;
20. Significant acute or chronic medical illness that could be negatively impacted by the electroporation treatment as deemed by the investigator;
21. Current or history of clinically significant, medically unstable disease which, in the judgement of the investigator, would jeopardize the safety of the subject, interfere with study assessments or endpoint evaluation, or otherwise impact the validity of the study results (e.g. chronic renal failure, angina, myocardial ischemia or infarction, class 3 or higher congestive heart failure, cardiomyopathy, or clinically significant arrhythmias);
22. Malignancy or treatment for malignancy within 2 years of screening, with the exception of superficial skin cancers that only require local excision;

23. Acute or chronic bleeding or clotting disorder that would contraindicate IM injections or use of blood thinners (e.g. anticoagulants or antiplatelet drugs) within 2 weeks of Day 0;
24. History of seizures unless seizure free for 5 years with the use of one or fewer antiepileptic agents;
25. Sustained, manually confirmed, sitting systolic blood pressure >150 mm Hg or <90 mm Hg or a diastolic blood pressure >95 mm Hg at Screening or Day 0;
26. Resting heart rate <50 bpm (unless attributable to athletic conditioning) or >100 bpm at Screening or Day 0;
27. Prior major surgery within 4 weeks of Day 0;
28. Participated in an interventional study with an investigational compound or device within 4 weeks of signing informed consent (participation in an observational study is permitted);
29. Less than two acceptable sites available for IM injection considering the deltoid and anterolateral quadriceps muscles;
30. Tattoos, keloids or hypertrophic scars located within 2 cm of intended treatment site;
31. Cardioverter-defibrillator or pacemaker (to prevent a life-threatening arrhythmia) that is located in ipsilateral deltoid injection site (unless deemed acceptable by a cardiologist);
32. Metal implants or implantable medical device within the intended treatment site (i.e. electroporation area);
33. Active drug or alcohol use or dependence that, in the opinion of the investigator, would interfere with adherence to study requirements;
34. Prisoner or subject who is compulsorily detained (involuntarily incarcerated) for treatment of either a psychiatric or physical (i.e. infectious disease) illness;
35. Active military service personnel;
36. Study-related staff or family members of study-related staff;
37. Any illness or condition that in the opinion of the investigator may affect the safety of the subject or the evaluation of any study endpoint.

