### 6.15 CONCOMITANT MEDICATIONS/TREATMENTS

All medications (prescription and nonprescription) taken within 8 weeks prior to screening biopsy date of eligible subjects must be recorded on the CRF. Actual or estimated start and stop dates must be provided. Medical procedures performed within 8 weeks prior to screening biopsy date of eligible subjects that do not affect subject’s eligibility for participation and during the study (including over the counter or herbal), will be recorded on the CRFs. This information will be obtained from the subject and abstracted from any available medical records. The indication for the medication, dose, and dose regimen will be documented. Medication that is considered necessary for the subject’s safety and well-being may be given at the discretion of the investigator and recorded in the appropriate sections of the CRF.

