### 6.16 RESTRICTIONS

The following medications and treatments are prohibited:

- Previous treatment with imiquimod for vulvar HSIL within 4 weeks prior to screening
- Long term use ( $\geq 7$  days) of oral or parenteral glucocorticoids at a dose of  $\geq 20$  mg/day of prednisone equivalent (use of inhaled, nasal, otic and ophthalmic corticosteroids are allowed)
- Disease modifying doses of anti-rheumatic drugs (e.g., azathioprine, cyclophosphamide, cyclosporine, methotrexate), and biologic disease modifying drugs such as TNF- $\alpha$  inhibitors (e.g. infliximab, adalimumab or etanercept) at screening and throughout the study
- Administration of any non-study related, non-live vaccine within 2 weeks of any study treatment or within 4 weeks of any study treatment for any non-study related live vaccine
- Blood thinners/Anticoagulants within 2 weeks of any study treatment

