### 3.2.1 DEFINITION OF RESPONDER AND NON-RESPONDER

Responder and non-responder definitions ([Table 4](#)) take into account both histopathologic regression of vulvar HSIL and virologic (HPV-16/18) clearance from tissue samples since HPV persistence is an important factor in the clinical progression of HSIL.

A treatment responder is defined as a subject with no histologic evidence of vulvar HSIL and no evidence of HPV-16 or HPV-18 in vulvar tissue at evaluation and who did not receive non-study related medication for treatment of VIN lesions. A treatment non-responder is a subject with histologic evidence of vulvar HSIL, adenocarcinoma-in-situ, or vulvar carcinoma at evaluation, and/or a subject with evidence of HPV-16/18 at evaluation, or a subject who received non-study related medications for treatment of VIN lesions. Any

case of histologically confirmed progression is considered a non-responder. Progression is defined as advancement to carcinoma by histology.

Table 4: Definition of Responder and Non-responder	
Responder	Non-Responder
Subject with no histologic evidence of vulvar HSIL a AND Subject with no evidence of HPV-16 or HPV-18 in vulvar tissue at evaluation AND Subject who did not receive non-study related medication for treatment of VIN lesions.	Subject with histologic evidence of vulvar HSIL, Adenocarcinoma-in-situ (AIS), vulvar carcinoma at evaluation  AND/OR Subject with evidence of HPV-16 or HPV-18 in vulvar tissue at evaluation  OR Subject who received non-study related medication for treatment of VIN lesions

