## 5. STUDY TREATMENT

### 5.1 INVESTIGATIONAL PRODUCTS

The VGX-3100 drug product contains DNA plasmids for expression of HPV-16 E6/E7 (pGX3001) and HPV-18 E6/E7 (pGX3002) antigens that have been designed and constructed using proprietary synthetic consensus DNA (SynCon®) technology. The VGX-3100 formulation to be used in this study is described in [Table 5](#) and will be presented in a clear glass vial for intramuscular injection.

Imiquimod 5% is a topical cream for external use and is supplied in single-use packets containing 250 mg of cream. Each gram of the 5% cream contains 50 mg of imiquimod in an off-white oil-in-water vanishing cream base. Inactive ingredients include benzyl alcohol, cetyl alcohol, glycerin, methylparaben, oleic acid, oleyl alcohol, polysorbate 60, propylparaben, purified water, stearyl alcohol, sorbitan monostearate, white petrolatum, and xanthan gum. There are 24 single-use packets of imiquimod in one box. The product manufacturer is Perrigo, Yeruham 80500, Israel.

Imiquimod is indicated for the treatment of external genital and perianal warts/condyloma acuminata in patients 12 year old or older. Although it is not approved by the US Food and Drug Administration for the treatment of vulvar HSIL, imiquimod is currently

recommended as a non-surgical, off-label treatment option for vulvar dysplasia by the American College of Obstetricians and Gynecologists (ACOG).

VGX-3100 and imiquimod will be provided by Inovio Pharmaceuticals, Inc. or its designee.

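### Table 4 disqualifies non-study medication by its indication, so non-study imiquimod used on vulvar warts in the VGX-3100-alone arm can still be scored as response

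*Protocol*

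**What the plan says.** **Responder rule.** Protocol 3.2.1, Table 4, requires clear histology, no detectable HPV-16/18, and a "Subject who did not receive non-study related medication for treatment of VIN lesions". The synopsis repeats the rule.

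**Entry.** In 4.2, criterion 11 excludes "Treatment for genital warts within 4 weeks prior to screening". Criteria 2 to 4 exclude neoplasia at other sites only when it is untreated: "Biopsy-proven Vaginal Intraepithelial Neoplasia (VAIN) and are not undergoing treatment for VAIN", "Biopsy-proven Anal Intraepithelial Neoplasia (AIN) and are not undergoing treatment for AIN" and "Biopsy-proven Cervical Intraepithelial Neoplasia (CIN) 2/3 and are not undergoing treatment for CIN". Treated women are eligible, and the kind of treatment is not limited.

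**On-study medication.** The only imiquimod entry on the prohibited list in 6.16 is "Previous treatment with imiquimod for vulvar HSIL within 4 weeks prior to screening". Under 6.15, medication judged necessary for the woman's safety and well-being "may be given at the discretion of the investigator and recorded in the appropriate sections of the CRF".

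**Imiquimod.** Section 5.1 states: "Imiquimod is indicated for the treatment of external genital and perianal warts/condyloma acuminata in patients 12 year old or older". Section 1.1.14 describes it as effective for vulvar HSIL on the strength of randomised trials.

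**Analysis.** Section 8.9 tests each arm separately against 2% at one-sided 0.025. Section 8.3 assumes response rates of 20% (alone) and 28% (combination), with 90% evaluable at Week 48.

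The text of version 1.2 at hand stops at 6.12, so 6.15, 6.16 and section 8 are read from version 1.1. The version 1.2 change list names only removal of the WOMAN-PRO instrument and calls all other changes administrative.

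**The concern.** Imiquimod is what distinguishes the two arms, and the protocol itself regards it as active against the lesion that defines the endpoint. The condition on outside medication is there to stop another treatment's effect being credited to VGX-3100. Because it is tied to indication, it fails when the same active cream reaches the vulva for another reason, and warts are the reason that the protocol itself supplies. Condyloma also counts as absence of HSIL on histology, so warts and a histologic response can coexist.

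The benchmark is 2% and the arm is small. One or two responses that are not due to VGX-3100 weigh heavily in a rule that needs three.

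**Working it through.** **1. What happens to one woman under the stated rules**

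Take a woman randomised to VGX-3100 alone who uses non-study imiquimod on vulvar warts between Day 0 and Week 48, and whose Week 48 tissue is clear.

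- Criterion 11 looks back 4 weeks from screening, so it does not reach her.
- The imiquimod entry in 6.16 concerns earlier use for vulvar HSIL, so it does not reach her. The same list carries on-study bars for anti-rheumatic drugs, vaccines and anticoagulants.
- Table 4 asks whether the medication was for VIN. It was for warts, so she is a responder.
- The per-protocol set (8.4) removes protocol violations. Her use is not written as one, so that set would not clearly remove her.

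**2. Decision rule and the plan's own power**

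Inputs: 24 and 12 randomised, 90% evaluable, null rate 0.02, one-sided 0.025. Evaluable numbers: 24 × 0.9 = 21.6 and 12 × 0.9 = 10.8, or about 22 and 11. The rule is the smallest r with P(X ≥ r | n, 0.02) < 0.025, exact binomial.

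| Arm | n | r | P(X ≥ r) at 2% | Power at planned rate |
|---|---|---|---|---|
| Alone | 22 | 3 | 0.0093 | 84.6% at 20% |
| Alone | 21 | 3 | 0.0081 | 82.1% at 20% |
| Combination | 11 | 2 | 0.0195 | 85.8% at 28% |
| Combination | 10 | 2 | 0.0162 | 81.7% at 28% |

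In the alone arm r = 2 is not enough, since P(X ≥ 2 | 22, 0.02) = 0.071. Read as at least 80%, the stated power holds in both arms and is not in question here.

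**3. False success in the alone arm when VGX-3100 does nothing**

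Let q be the probability that a user meets the composite endpoint (HSIL gone and HPV-16/18 undetectable). All other women respond at 2%.

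- One user: q·P(X₂₁ ≥ 2) + (1 − q)·P(X₂₁ ≥ 3) = q(0.0653) + (1 − q)(0.0081).
- Two users: q²·P(X₂₀ ≥ 1) + 2q(1 − q)·P(X₂₀ ≥ 2) + (1 − q)²·P(X₂₀ ≥ 3) = q²(0.3324) + 2q(1 − q)(0.0599) + (1 − q)²(0.0071).

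The documents give neither the number of users nor q, so both are assumptions. The value q = 10% is the 2% null plus the plan's own increment for adding imiquimod (28% − 20% = 8 points). The value q = 28% is the full planning rate of the combination arm.

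| q (assumed) | One user | Two users |
|---|---|---|
| 2% (no effect) | 0.9% | 0.9% |
| 10% | 1.4% | 2.0% |
| 20% | 2.0% | 3.7% |
| 28% | 2.4% | 5.4% |
| 100% (extreme) | 6.5% | 33% |

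Example, two users at 28%: 0.0784 × 0.3324 + 0.4032 × 0.0599 + 0.5184 × 0.0071 = 0.0261 + 0.0242 + 0.0037 = 0.054.

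**The case against.** **Criteria 2 to 4.** A reader might infer that the entry criteria admit women already on imiquimod for VAIN, AIN or CIN. The documents do not support that. No section says that treatment at those sites is imiquimod or topical. The cream is described as for external use, and its stated effect in vulvar HSIL comes from applying it to the affected area. These criteria leave a question open and no more. The vulvar wart case rests on the protocol's own text.

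**Silence.** A reader might say that the protocol allows wart treatment on study. It does so only by not forbidding it. Exclusion 37 lets an investigator turn away a woman whose condition could affect endpoint evaluation, but it is discretionary, acts at entry and does not cover treatment begun later.

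**Recording.** Section 6.15 has the indication recorded for each medication, so users could be found and a sensitivity analysis run. That is fair, but the primary analysis would still count them as responders under Table 4. The responder definition is fixed in the protocol, not left to the SAP.

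**Alone versus combination.** A reader might infer that a planned comparison is damaged. No between-arm test is specified, so any blurring is descriptive.

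**Size.** The 6.5% and 33% figures require one or two women certain to meet the full composite because of the cream. One or two users is a much weaker condition. This objection stands, and those figures are extremes only.

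**Version.** The 6.16 and 6.15 text of version 1.2 cannot be seen. The change list makes a substantive difference unlikely but does not exclude one.

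**Conclusion.** The point holds for one route: non-study imiquimod, or another agent active against vulvar HSIL, applied to the vulva for an indication other than VIN. Table 4 scores such a woman as a responder if her tissue is clear, and no stated rule stands in the way.

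The inflation is modest under plausible assumptions. With no VGX-3100 effect, false success rises from 0.9% to 1.4–2.4% with one user, still within 2.5%. With two users it is 2.0–5.4%, which can exceed 2.5%. This assumes 22 evaluable women, a 2% rate in non-users and 10–28% response in users. How common such use would be is unknown. The matter is worth correcting because the bias runs only towards success and removing it takes only a change of wording.

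**What to change.** For the Week 48 endpoint, change Table 4 and the matching synopsis text so that the condition turns on agent and site. Non-study imiquimod, or another agent with activity against vulvar HSIL, applied to the vulva for any indication between Day 0 and the Week 48 biopsy counts as non-response in the primary analysis. Reconcile 4.2 (criteria 2 to 4 and 11), 6.15 and 6.16 with that rule. Which concomitant treatments to permit is the sponsor's clinical decision and is not proposed here.

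**Cost.** A wording amendment, with no new procedure. A few true VGX-3100 responders who used such an agent would be scored as non-responders. Of 22 evaluable women, one such user leaves 21 who can count, with power 82.1%. Two leave 20, with 79.4%. With no users it is 84.6%. False success stays at or below 0.9%.

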  - 31) Cardioverter-defibrillator or pacemaker (to prevent a life-threatening arrhythmia) that is located in ipsilateral deltoid injection site (unless deemed acceptable by a cardiologist);
  - 32) Metal implants or implantable medical device within the intended treatment site (i.e. electroporation area);
  - 33) Active drug or alcohol use or dependence that, in the opinion of the investigator, would interfere with adherence to study requirements;
  - 34) Prisoner or subject who is compulsorily detained (involuntarily incarcerated) for treatment of either a psychiatric or physical (i.e. infectious disease) illness;
  - 35) Active military service personnel;
  - 36) Study-related staff or family members of study-related staff;
  - 37) Any illness or condition that in the opinion of the investigator may affect the safety of the subject or the evaluation of any study endpoint.

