## 5.7 USE OF INVESTIGATIONAL DEVICE

The CELLECTRA® 2000 device and its components bear labels that identify the device name and place of business of the manufacturer. The CELLECTRA® 2000 User Manual describes all relevant contraindications, hazards, adverse effects, interfering substances or devices, warnings, and precautions. Each CELLECTRA® 2000 Pulse Generator has a unique serial number, and each CELLECTRA® 2000 Applicator has a unique serial number. Each CELLECTRA® 2000 Array has a Lot Number, Manufacture Date, and Expiration Date.

The treatment procedure must be performed by qualified personnel. Any individual designated to perform the procedure should be permitted by the relevant local authorities to administer parenteral injections to patients (e.g. MD, DO, RN) in addition to successfully completing device training from sponsor personnel. Individuals whose credentials do not meet the relevant local requirements may perform the treatment procedure under both of the conditions below:

[figure not shown]
[figure not shown]
1. The procedure must be performed under the direct supervision of the Investigator or an approved Sub-Investigator who has already been trained by the sponsor's personnel.
2. The CV and any relevant qualifications of the individual must be reviewed and approved by the sponsor or its designee to perform the procedure.

Any deviation from the above procedures must be approved by the sponsor or its designee.

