## 6. STUDY PROCEDURES AND TREATMENTS

This section lists the procedures and parameters for each planned study evaluation. The timing of each assessment is listed in the Schedule of Events Table (see [Table 1](#)).

A subject will be required to provide informed consent for use of any information collected prior to consenting and before any additional study specific procedures are performed.

Protocol waivers or exemptions will not be granted with the exception of immediate safety concerns. Therefore, adherence to the study design requirements, including those specified in the Schedule of Events Table are essential and required for study conduct.

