## 6.4 INJECTION AND ELECTROPORATION (EP)

Subjects will receive four doses of VGX-3100 (6 mg DNA/dose) in a volume of 1 mL by intramuscular injection in the deltoid or lateral quadriceps muscles (preferably deltoid) followed immediately by EP with the CELLECTRA® 2000. Study treatment plus EP must not be given within 2 cm of a tattoo, keloid or hypertrophic scar, or if there is implanted metal within the same limb. Any device implanted in the chest (e.g., cardiac pacemaker, defibrillator or retained leads following device removal) excludes the use of the deltoid muscle on the same side of the body. The timing of the initial dose will be designated Day 0 with the subsequent doses scheduled for administration at Weeks 4, 12, 24, and at Weeks 52 and 78 for Subgroups C and D only.

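### The cardiologist exception in exclusion criterion 31 can be read as permission to electroporate a deltoid that Section 6.4 bars without exception

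*Protocol*

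**What the plan says.** All of the text below stands in the current protocol version, 1.2.

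- **Section 4.2, criterion 31:** excludes a "Cardioverter-defibrillator or pacemaker (to prevent a life-threatening arrhythmia) that is located in ipsilateral deltoid injection site (unless deemed acceptable by a cardiologist"). The synopsis copy carries the same exception: "located in ipsilateral deltoid injection site (unless deemed acceptable by a cardiologist").
- **Section 6.4, chest devices:** "Any device implanted in the chest (e.g., cardiac pacemaker, defibrillator or retained leads following device removal) excludes the use of the deltoid muscle" on that side. No exception is given.
- **Section 6.4, metal:** treatment plus electroporation "must not be given within 2 cm of a tattoo, keloid or hypertrophic scar, or if there is implanted metal within the same limb". Again no exception is given.
- **Section 4.2, criterion 32:** excludes "Metal implants or implantable medical device within the intended treatment site (i.e. electroporation area"), with no role for a cardiologist.
- **Section 6, opening text:** "Protocol waivers or exemptions will not be granted with the exception of immediate safety concerns".
- **Section 3.1 and Section 4.2, criterion 29:** the deltoid is the preferred site and the anterolateral quadriceps the alternate. A woman with fewer than two acceptable sites is excluded.
- **Section 5.7:** the device "User Manual describes all relevant contraindications, hazards, adverse effects, interfering substances or devices, warnings, and precautions". The manual itself is not among the documents.

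**The concern.** Eligibility is settled from the criteria list, and the rule on where a dose may go sits in a different section. Criterion 31 does not refer to 6.4. A site with a cardiologist's clearance on file therefore has wording in the eligibility list that appears to support injecting and electroporating the deltoid beside a pacemaker or defibrillator, in a trial where the deltoid is the preferred site. Section 6.4 forbids exactly that.

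What is at stake is patient safety. Table 9 lists disrupted function of implanted electronic devices among risks of unknown frequency or theoretical risks, on condition that the electroporation device is not used according to its User Manual. The protocol thus recognises the hazard in one place while another place appears to relax the safeguard. Criterion 31 also leaves out retained leads, which 6.4 names.

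**Working it through.** There is no figure in the plan to reproduce, so the check sets the rules side by side.

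**Step 1: what triggers criterion 31.** The criterion refers to a device at the ipsilateral deltoid injection site. Read literally, it applies only when that deltoid is the intended site.

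**Step 2: the possible cases.**

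| Device and planned site | Criterion 31 | Other rules |
|---|---|---|
| Device in the chest, same-side deltoid planned | Excluded unless a cardiologist accepts | 6.4 bars this deltoid, no exception |
| Device lying in the deltoid itself, that deltoid planned | Excluded unless a cardiologist accepts | 6.4 bars the limb for implanted metal, and criterion 32 excludes; neither has an exception |
| Opposite deltoid or a quadriceps planned | Not triggered on a literal reading; on a looser reading, clearance admits the woman | 6.4 permits dosing if the chosen site itself meets its rules |

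In the first two rows, a site that takes the clearance as permission to inject breaks 6.4. In the third row both texts are obeyed.

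**Step 3: could the clearance override 6.4?** No. Section 6 rules out waivers except for immediate safety concerns, and a clearance given for convenience of site is not one.

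**Step 4: is dosing elsewhere feasible?** Assume four candidate sites, with left and right counted separately. Section 6.1.2 names the right and left deltoids separately, but criterion 29 does not say how sites are counted.

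- Sites: 2 deltoids + 2 quadriceps = 4.
- Device or leads on one side of the chest: 4 − 1 = 3 sites left.
- Devices or leads on both sides: 4 − 2 = 2 sites left.

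Criterion 29 excludes below 2, so chest devices alone do not trigger it. This shows that the safe route is open. It is not a measure of harm.

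**Step 5: how often the choice of site arises.** There are 4 scheduled doses, and at most 4 + 2 = 6 for women in Subgroups C and D who receive both optional doses. This is the dosing schedule and not an event rate.

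**The case against.** The strongest reply is that the two texts do different jobs. Criterion 31 decides who may enter and 6.4 decides where each dose goes. A site can obtain a cardiologist's clearance, enrol the woman, dose the opposite deltoid or a quadriceps, and break neither rule. The protocol provides for this through the alternate site and criterion 29. Operators must also complete sponsor device training (Section 5.7), and 6.4 is explicit. A wrong dose would require a site to read criterion 31 as permission and ignore 6.4.

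The group is also very small. Enrolment is about 36. Inclusion criterion 10 (ECG) and exclusion criteria 20, 21 and 37 remove some women with cardiac disease, although several rest on investigator judgement and none excludes every woman with a stable device. The harm described in Table 9 depends on departure from a manual that cannot be checked here.

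Most of this stands, and it limits the point. A reader might infer that the exception is void, or that it permits only what 6.4 forbids. The documents do not support that. It follows only from a strictly literal reading of a loosely worded criterion, since a pacemaker would not ordinarily sit in a deltoid injection site, and it leaves out the use of clearance for enrolment with dosing elsewhere.

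What the reply does not remove is the gap in the text. Criterion 31 nowhere says that clearance concerns enrolment only, and it does not point to 6.4. Sites should not have to work out for themselves which of two device-safety statements prevails.

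**Conclusion.** The point holds as a drafting inconsistency in a device-safety rule. The exception in criterion 31 can be read as allowing use of a deltoid that 6.4 bars, and nothing in the text shown reconciles the two. A site that follows 6.4 stays safe.

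The situation should be rare; its frequency cannot be estimated because the protocol gives no number of device carriers. Sample size, power, type I error and the primary analysis are not affected. The conclusion rests on the wording of criterion 31, criterion 32 and Section 6.4. It does not depend on the four-site count. It would change in one respect if the User Manual allowed an exception: 6.4 would then be the text to amend.

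One nearby difference should not be counted as a second conflict. Criterion 32 refers to metal in the electroporation area and 6.4 to metal in the same limb. Both can be obeyed by dosing another limb.

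**What to change.** In criterion 31 (Section 4.2) and its synopsis copy, do one of the following:

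- delete the parenthesis that gives the decision to a cardiologist; or
- keep it for enrolment only and add: *Cardiologist clearance does not permit use of a site barred by Section 6.4; dose the contralateral deltoid or a quadriceps.*

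The second option keeps the cardiologist's review, which the first removes. If the device User Manual supports a true exception for the same-side deltoid, state it in 6.4 as well, so that both sections agree.

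Two things should be avoided. Do not add a statement that such a woman remains eligible, because it could be read as bypassing criteria 20, 21, 29, 32 and 37, which continue to apply. Do not turn the same-limb metal rule of 6.4 into an exclusion, since it governs where a dose is given and would needlessly exclude women who can be dosed in another limb.

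The cost is one reworded criterion, its synopsis copy and the eligibility checklist. With the enrolment-only wording, and on the four-site assumption, chest devices alone add no screen failures through criterion 29.
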